Complete and attach the required [Study Device Form](#), picking the "Study Device Form" for the document type. Any applicable device documentation (e.g., Manufacturer information; patient information packet; approved labeling; FDA correspondence, etc.) should be attached using "Other Device Documentation" for the document type.

Attachments

RESEARCH SITES

0 unresolved
comment(s)

To complete this section, ensure the responses are accurate then click "SAVE".

A) Check all the applicable sites listed below at which the research will be conducted. If none apply, you do not need to check any boxes.

UK Sites

UK Classroom(s)/Lab(s)
 UK Clinics in Lexington
 UK Clinics outside of Lexington
 UK Healthcare Good Samaritan Hospital
 UK Hospital

Schools/Education Institutions

Fayette Co. School Systems *
 Other State/Regional School Systems
 Institutions of Higher Education (other than UK)

***Fayette Co. School systems, as well as other non-UK sites, have additional requirements that must be addressed. See ORI's [IRB Application Instructions - Off-site Research](#) web page for details.**

Other Medical Facilities

Bluegrass Regional Mental Health Retardation Board
 Cardinal Hill Hospital
 Eastern State Hospital
 Norton Healthcare
 Nursing Homes
 Shriner's Children's Hospital
 Veterans Affairs Medical Center
 Other Hospitals and Med. Centers

Correctional Facilities
 Home Health Agencies
 International Sites

Research activities conducted at performance sites that are not owned or operated by the University of Kentucky, at sites that are geographically separate from UK, or at sites that do not fall under the UK IRB's authority, are subject to special procedures for coordination of research review. Additional information is required (see [IRB Application Instructions - Off-Site Research](#) web page), including:

- A letter of support and local context is required from non-UK sites. See *Letters of Support and Local Context* on the [IRB Application Instructions - Off-Site Research](#) web page for more information.
- Supportive documentation, including letters of support, can be attached below.
- NOTE: If the non-UK sites or non-UK personnel are engaged in the research, there are additional federal and university requirements which need to be completed for their participation. For instance, the other site(s) may need to complete their own IRB review, or a cooperative review arrangement may need to be established with non-UK

sites.

- Questions about the participation of non-UK sites/personnel should be discussed with the ORI staff at [contact].

List all other non-UK owned/operated locations where the research will be conducted:

Describe the role of any non-UK site(s) or non-UK personnel who will be participating in your research.

Attachments

B) Is this a multi-site study for which **you are the lead investigator or UK is the lead site?** Yes No

If YES, describe the plan for the management of reporting unanticipated problems, noncompliance, and submission of protocol modifications and interim results from the non-UK sites:

C) If your research involves collaboration with any sites and/or personnel outside the University of Kentucky, then it is considered multisite research and IRB reliance issues will need to be addressed. This may include national multi-center trials as well local studies involving sites/personnel external to UK. If you would like to request that the University of Kentucky IRB (UK IRB) serve as the lead IRB for your study, or if you would like the UK IRB to defer review to another IRB, please contact the [contact].

RESEARCH ATTRIBUTES

0 unresolved
comment(s)

Indicate the items below that apply to your research. Depending on the items applicable to your research, you may be required to complete additional forms or meet additional requirements. Contact the ORI [contact]) if you have questions about additional requirements.

Not applicable

Check All That Apply

- Academic Degree/Required Research
- Alcohol/Drug/Substance Abuse Research
- Biological Specimen Bank Creation (for sharing)
- Cancer Research
- CCTS-Center for Clinical & Translational Science
- Certificate of Confidentiality
- Clinical Research
- Clinical Trial - Phase 1
- Clinical Trial
- Collection of Biological Specimens for internal banking and use (not sharing)
- Community-Based Participatory Research
- Deception
- Educational/Student Records (e.g., GPA, test scores)
- Emergency Use (Single Patient)
- Gene Transfer
- Genetic Research
- GWAS (Genome-Wide Association Study) or NIH Genomic Data Sharing (GDS)
- Human Cells, Tissues, and Cellular and Tissue Based Products
- Individual Expanded Access or Compassionate Use
- International Research
- Planned Emergency Research Involving Exception from Informed Consent
- Recombinant DNA
- Registry or data repository creation
- Stem Cell Research
- Suicide Ideation or Behavior Research
- Survey Research
- Transplants
- Use, storage and disposal of radioactive material and radiation producing devices
- Vaccine Trials

For additional requirements and information:

- [Cancer Research \(MCC PRMC\)](#)
- [Certificate of Confidentiality](#) (look up "Confidentiality/Privacy...")
- [CCTS \(Center for Clinical and Translational Science\)](#)
- [Clinical Research](#) (look up "What is the definition of....")
- [Clinical Trial](#)
- [Collection of Biological Specimens for Banking](#) (look up "Specimen/Tissue Collection...")
- [Collection of Biological Specimens](#) (look up "Specimen/Tissue Collection...")
- [Community-Based Participatory Research](#) (look up "Community-Engaged...")
- [Data & Safety Monitoring Board \(DSMB\)](#)

*For Medical IRB: [Service Request Form](#) for CCTS DSMB

- [Data & Safety Monitoring Plan](#)
- [Deception*](#)

*For deception research, also go to the E-IRB Application Informed Consent section, checkmark and complete "Request for Waiver of Informed Consent Process"

- [Emergency Use \(Single Patient\) \[attach Emergency Use Checklist\]](#) (PDF)
- [Genetic Research](#) (look up "Specimen/Tissue Collection...")
- [Gene Transfer](#)
- [HIV/AIDS Research](#) (look up "Reportable Diseases/Conditions")
- [Screening for Reportable Diseases \[E2.0000\]](#) (PDF)
- [International Research](#) (look up "International & Non-English Speaking")
- [NIH Genomic Data Sharing \(GDS\) Policy](#) (PDF)
- [Planned Emergency Research Involving Waiver of Informed Consent*](#)

*For Planned Emergency Research Involving Waiver of Informed Consent, also go to the E-IRB Application Informed Consent section, checkmark and complete "Request for Waiver of Informed Consent Process"

- [Use, storage and disposal of radioactive material and radiation producing devices](#)

FUNDING/SUPPORT

0 unresolved
comment(s)

If the research is being submitted to, supported by, or conducted in cooperation with an external or internal agency or funding program, indicate below all the categories that apply. 

Not applicable

Check All That Apply

- Grant application pending
- (HHS) Dept. of Health & Human Services
 - (NIH) National Institutes of Health
 - (CDC) Centers for Disease Control & Prevention
 - (HRSA) Health Resources and Services Administration
 - (SAMHSA) Substance Abuse and Mental Health Services Administration
- (DoJ) Department of Justice or Bureau of Prisons
- (DoE) Department of Energy
- (EPA) Environmental Protection Agency
- Federal Agencies Other Than Those Listed Here
- Industry (Other than Pharmaceutical Companies)
- Internal Grant Program w/ proposal
- Internal Grant Program w/o proposal
- National Science Foundation
- Other Institutions of Higher Education
- Pharmaceutical Company
- Private Foundation/Association
- U.S. Department of Education
- State

Other:

Click applicable listing(s) for additional requirements and information:

- [\(HHS\) Dept. of Health & Human Services](#)
- [\(NIH\) National Institutes of Health](#)
- [\(CDC\) Centers for Disease Control & Prevention](#)
- [\(HRSA\) Health Resources & Services Administration](#)
- [\(SAMHSA\) Substance Abuse & Mental Health Services Administration](#)
- Industry (Other than Pharmaceutical Companies) [[IRB Fee Info](#)]
- [National Science Foundation](#)
- [\(DoEd\) U.S. Department of Education](#)
- [\(DoJ\) Department of Justice or Bureau of Prisons](#)
- [\(DoE\) Department of Energy Summary and Department of Energy Identifiable Information Compliance Checklist](#)
- [\(EPA\) Environmental Protection Agency](#)

Specify the funding source and/or cooperating organization(s) (e.g., National Cancer Institute, Ford Foundation, Eli Lilly & Company, South Western Oncology Group, Bureau of Prisons, etc.):

- University of Kentucky Center for Clinical and Translational Science grant
- Orthopaedic Trauma Association grant

Add Related Grants

If applicable, please search for and select the OSPA Account number or Electronic Internal Approval Form (eIAF) # (notif #) associated with this IRB application using the "Add Related Grants" button.
If required by your funding agency, upload your grant using the "Grant/Contract Attachments" button.

[Add Related Grants](#)

[Grant/Contract Attachments](#)

The research involves use of Department of Defense (DoD) funding, military personnel, DoD facilities, or other DoD resources. (See [DoD SOP](#) and [DoD Summary](#) for details)

Yes No

Using the “attachments” button (below), attach applicable materials addressing the specific processes described in the DoD SOP.

[DOD SOP Attachments](#)

Additional Certification: (If your project is federally funded, your funding agency may request an Assurance/ Certification/Declaration of Exemption form.) Check the following if needed:

Protection of Human Subjects Assurance/Certification/Declaration of Exemption (Formerly Optional Form – 310)

[Assurance/Certification Attachments](#)

OTHER REVIEW COMMITTEES

0 unresolved
comment(s)

If you check any of the below committees, additional materials may be required with your application submission.

Does your research fall under the purview of any of the other review committees listed below? [If yes, check all that apply and attach applicable materials using the attachment button at the bottom of your screen.]

Yes No

Additional Information

- Institutional Biosafety Committee
- Radiation Safety Committee
- Radioactive Drug Research Committee
- Markey Cancer Center (MCC) Protocol Review and Monitoring Committee (PRMC)
- Graduate Medical Education Committee (GME)
- Office of Medical Education (OME)

- [Institutional Biosafety Committee \(IBC\)](#) - Attach required IBC materials
- [Radiation Safety Committee \(RSC\)](#) - For applicability, see instructions and attach form
- [Radioactive Drug Research Committee \(RDRC\)](#)
- [Markey Cancer Center \(MCC\) Protocol Review and Monitoring Committee \(PRMC\)**](#) - Attach MCC PRMC materials, if any, per instructions.
- [Office of Medical Education \(OME\)](#)
- [Graduate Medical Education Committee \(GME\)](#)

Attachments

**** If your study involves cancer research, be sure to select "Cancer Research" in the "Research Attributes" section.** ORI will send your research protocol to the Markey Cancer Center (MCC) Protocol Review and Monitoring Committee (PRMC). The [MCC PRMC](#) is responsible for determining whether the study meets the National Cancer Institute (NCI) definition of a clinical trial and for issuing documentation to you (the investigator) which confirms either that PRMC approval has been obtained or that PRMC review is not required. Your IRB application will be processed and reviewed independently from the PRMC review.

ADDITIONAL INFORMATION/MATERIALS

0 unresolved
comment(s)

Do you want specific information inserted into your approval letter? Yes No

Approval Letter Details:

If you wish to have specific language included in your approval letter (e.g., serial #, internal tracking identifier, etc...), type that language in the box below exactly as it should appear in the letter. The text you enter will automatically appear at the top of all approval letters, identical to how you typed it, until you update it. Don't include instructions or questions to ORI staff as those will appear in your approval letter. **If these details need to be changed for any reason, you are responsible for updating the content of this field.**

Additional Materials:

If you have other materials you would like to include for the IRB's consideration, check all that apply and attach the corresponding documents using the Attachments button below.

Detailed protocol
 Dept. of Health & Human Services (DHHS) approved protocol (such as NIH sponsored Cooperative Group Clinical Trial)
 Other Documents

Protocol/Other Attachments

Attach Type	File Name
Other	Signed Inflammatory Marker Protocol Violation Letter.pdf
Other	Subject Enrollment Memo for IRB.docx
Protocol	CCTS Full Research Proposal.pdf
Protocol	OTA Full Grant Application.pdf
Protocol	IM Study- Protocol Changed- Clean.docx
Protocol	IM AE Risk Mitigation Plan Formal 4.17.20.docx

NOTE: [Instructions for Dept. of Health & Human Services \(DHHS\)-approved protocol](#)

If you have password protected documents, that feature should be disabled prior to uploading to ensure access for IRB review.

To view the materials currently attached to your application, click "All Attachments" on the left menu bar.

SIGNATURES (ASSURANCES)**0 unresolved comment(s)****Introduction**

All IRB applications require additional assurances by a Department Chairperson or equivalent (DA), and when applicable, a Faculty Advisor or equivalent (FA). This signifies the acceptance of certain responsibilities and that the science is meritorious and deserving of conduct in humans. The person assigned as DA *should not* also be listed in the Study Personnel section, and the individual assigned as FA *should* be listed in the Study Personnel section.

For a list of responsibilities reflected by signing the Assurance Statement, refer to ["What does the Department Chairperson's Assurance Statement on the IRB application mean?"](#)

For a detailed illustration of how to complete this section, please review the short online video tutorial ["Signatures \(Assurance\) Section - How to Complete."](#) Otherwise, follow the steps below.

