Aim 1: The study population will consist of 200 patients (100 control, 100 treated with Ketorolac) that are admitted to the inpatient surgical service at our level I trauma centers for management of orthopedic trauma care. All trauma patients that are between the ages of 18-75 and with NISS > 9 (moderate injury) [33, 34] will be enrolled and treated according to the standard Advance Trauma Life Support (ATLS) protocol. 100 patients in the control group will receive placebo intravenous saline every 6 hours for their initial 5 days of hospitalization and no NSAID administration. 100 patients randomized to the treatment group will receive 15 mg of Ketorolac every 6 hours for their initial 5 days of hospitalization. A daily blood sample (10 cc) will be collected on Days 1–5 by blinded health care personnel. These blood samples will be analyzed via sandwich ELISA method for concentrations of IL-1, IL-6, IL-10, and PGE2. Serum concentrations will be compared between the treatment and control groups using two-tailed independent t-tests. In addition to the standard trauma labs, patient demographics, injury data (gender, age, BMI, mechanism of injury, NISS, and types of surgical/procedural interventions), injury outcomes (incidence of bacterial pneumonia, ARDS, SIRS, MODS), complications defined in the National Trauma Dataset, and inflammatory data will be compiled, tracked, and maintained in our clinical database (REDCap). Outcome variables (hospital and ICU length of stay and occurrence of pneumonia and/or ARDS and/or SIRS or death), and the predictor variables of interest (inflammatory markers and NISS) will be compared using Poisson regression. The odds of developing post traumatic complications in the different predictor groups will be determined using multiple logistic regressions. The covariates will be adjusted for in the regression models: age, sex, injury severity, severity of head and/or extremity injury, injury mechanism, and injury outcome.

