		Day 1	Day 2	Day 3	Day 4	Day 5	Discharge	2 Week	6 Week	3 Month	6 Month	12 Month
Inclusion/Exclusion Review	X											
Informed Consent	X											
Blood Sample		X	X	X	X	X						
Ketorolac Intervention		X	X	X	X	X						
MME		X	X	X	X	X	X					
VAS		X	X	X	X	X	X	X	X	X	X	X
Post-Traumatic Complications		X	X	X	X	X	X	X	X	X	X	X

10. Procedures Involved

- Patient identification:** Patients will be identified on morning intake rounds by the trauma team and the research staff who are present daily to screen and enroll patients.
- Screening/Enrollment:** Study population will consist of 112 patients (56 control, 56 treatment) admitted to the inpatient surgical service at University of Kentucky (UK) level I trauma center for management of trauma care. Trauma patients that are between the ages of 18-75 and with NISS > 9 (moderate injury) with anticipated admission of ≥ 5 days (to ensure completion of the treatment) will be enrolled (Grisoni et al., 2001; Stevenson, Segui-Gomez, Lescohier, Di Scala, & McDonald-Smith, 2001). All patients will be initially treated according to the standard Advance Trauma Life Support (ATLS) protocol and standard ICU protocols (if applicable). Experienced clinical research staff will prospectively identify patients who meet the inclusion criteria and none of the exclusion criteria detailed in table 2.
- Randomization:** Consented patients will be randomized using a computer-generated algorithm to the control group (1-2 mL of intravenous saline every 6 hours for 5 days after admission) or treatment group (15 mg of intravenous ketorolac every 6 hours for 5 days after admission).
- Treatment:** Ketorolac (15 mg) has been chosen as the treatment of choice for several reasons:
 - Ketorolac has a similar pharmacodynamics profile as indomethacin, which was used

in our previous animal model (Xiang et al., 2012).

(2) It is readily available intravenously obviating limitations of oral intake.

(3) In numerous prospective clinical studies, ketorolac infusion produced no change in cardiac or hemodynamic parameters in patients undergoing major vascular surgery (Camu, Van Overberge, Bullingham, & Lloyd, 1990; Peirce, Fragen, & Pemberton, 1990).

(4) 30 mg is the approved dose that is consistent with United States Food and Drug Administration (FDA) labeling per the package

(5) Ketorolac is part of the routine trauma acute pain protocol

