Patients with pre-existing medical co-morbidities and contraindications to ketorolac will be excluded from the study (see 5 for detailed exclusion criteria)

Patients in the treatment group will receive 15 mg IV ketorolac every 6 hours for 5 days after admission.

e. **Post-operative inpatient care:** Enrolled patients will have daily blood samples (10 cc) will be collected post-admission and at 24 hours intervals for 5 days by blinded health care personnel. The initial blood sample will be collected within 12 hours of initial injury and before the first scheduled administration of ketorolac to establish baseline cytokine profile. Subsequent blood sample collection will be 24 hours apart. Medication compliance and monitoring will be performed daily by the same research coordinators.

Sandwich ELISA will be used to determine the concentrations of IL-1, IL-6, IL-10, and PGE2 in obtained blood samples. Blinded quality control samples will be included in every batch for each ELISA assay. This will allow for the calculation of coefficient of variation (CV) within and across patient cohorts. In the present study, the CV will be calculated for IL-1, IL-6, IL-10, and PGE2. If wide variations are observed among the analytes during the analysis, we will restrict our analysis to analytes in which the CV is less than 20%.

In addition to the standard trauma labs (Sodium, Potassium, Creatinine, Lactic acid, Glucose, Platelet, blood urea nitrogen (BUN), hematocrit, and white blood cell count), patient demographics (sex, age, and BMI), injury data (mechanism of injury, NISS, and types of surgical/procedural interventions), posttraumatic complications (occurrence of bacterial pneumonia, ARDS, SIRS, MODS), complications defined in the National Trauma Dataset, and inflammatory data will be collected. This data will be maintained in our clinical database (REDCap) by a full-time Clinical Study Coordinator.

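### The application's marker regressions do not require a cytokine sample to precede the complication and leave out treatment arm, so post-onset, drug-altered values may serve as predictors

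*Combined protocol and SAP*

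**What the plan says.** The regressions appear only in the application text, under Research Description, Research Procedures, Aim 1.

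- Sampling: "A daily blood sample (10 cc) will be collected on Days 1–5 by blinded health care personnel". The analytes are IL-1, IL-6, IL-10 and PGE2.
- Outcomes: "Outcome variables (hospital and ICU length of stay and occurrence of pneumonia and/or ARDS and/or SIRS or death".
- Predictors and model: "the predictor variables of interest (inflammatory markers and NISS) will be compared using Poisson regression".
- Complications: "The odds of developing post traumatic complications in the different predictor groups will be determined using multiple logistic regressions".
- Adjustment: the list is age, sex, injury severity, severity of head or extremity injury, "injury mechanism, and injury outcome". Treatment arm is not on it.

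No sentence gives the sampling day, the summary (baseline, mean or peak), or the order of sample and event.

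In the protocol, Section 9, Table 1 marks the row "Post-Traumatic Complications" at Days 1-5, discharge, 2 and 6 weeks, and 3, 6 and 12 months. Section 10(e) takes the first sample "before the first scheduled administration of ketorolac to establish baseline cytokine profile" but does not link it to any regression. Section 7, the SAP, models cytokines as dependent variables, by time and group, in linear mixed models. It lists no regression of an outcome on a marker.

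**The concern.** A patient who develops pneumonia on Day 2 still gives samples on Days 3-5. If pneumonia raises IL-6, those values reflect the complication, yet the models allow them to be read as its predictor. An ever/never logistic model has no time order with which to detect this. SIRS makes the problem sharper, because it is itself a systemic inflammatory response.

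The second difficulty is the drug. Samples on Days 2-5 follow the start of treatment, and the application's Aim 1 asks whether ketorolac reduces the inflammatory cascade. If it does, later markers partly encode the arm. With arm left out, any effect of ketorolac on the outcome by another route would be credited to the marker.

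What is at stake is the interpretive claim. The background argues that adding cytokines to NISS improves prediction of length of stay. An association built on post-onset samples would seem to confirm that claim while measuring a consequence of complications.

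**Working it through.** **The plan's own figure.** The documents give no design figure for these regressions. The only calculation is for length of stay (Section 6), and it reproduces: n per group = 2(1.960 + 0.842)² × 1.5² / 0.928² = 41.0 by the normal formula, rounded up to 42 (41.995 with the t distribution). Then 84 / 0.75 = 112. I use N = 112 and two-sided alpha 0.05.

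**Assumed inputs (none is in the documents).** The marker has no true effect. Log marker SD is 0.8 between patients and 0.6 from day to day. A complication raises later samples by δ log units. Complication rate, onset window and δ vary.

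**Hand calculation for the 5-day mean.**

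1. SD of the mean = √(0.8² + 0.6²/5) = √0.712 = 0.844.
2. Let f be the average share of a case's five samples drawn after onset. With onset at any moment from Day 1 to Day 7, f = (0+1+2+3+4)/(6×5) = 0.333. With onset on a whole day 1-7 and only later days raised, f = (4+3+2+1)/(7×5) = 0.286. With whole days 1-14, f = 10/(14×5) = 0.143.
3. Spurious log odds ratio per SD: b = fδ/0.844.
4. Its standard error is about 1/√(Np(1−p)): 1/√(112×0.3×0.7) = 0.206 at 30% complications, and 1/√(112×0.15×0.85) = 0.265 at 15%.
5. False-positive rate = P(|Z + b/SE| > 1.96).

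| Setting | b | Odds ratio per SD | Hand, mean | Simulated, mean | Simulated, peak |
|---|---|---|---|---|---|
| 30%, any moment Days 1-7, δ 0.8 | 0.316 | 1.37 | 33% | 31% | 46% |
| 30%, whole days 1-7, δ 0.8 | 0.271 | 1.31 | 26% | 23-25% | 35-39% |
| 30%, whole days 1-14, δ 0.8 | 0.135 | 1.14 | 10% | 9-10% | 13-14% |
| 15%, whole days 1-14, δ 0.5 | 0.085 | 1.09 | 6% | 5-7% | 5-7% |

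The simulated columns are unadjusted logistic regressions. A range means repeated runs of the same setting. In the first setting, δ = 0.5 gives 14% (mean) and 18% (peak), and δ = 1.2 gives 57% and 83%. The Day 1 sample alone gives 4-5% and an odds ratio near 1.0.

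**A second set of assumptions** points the same way: within-patient correlation 0.6, 10-30% complications, 25-75% of them starting in Days 1-5, and a rise of 0.5-1.0 SD. At N = 112 the mean gives 5-55% and the peak 6-78%. In the middle scenario (20%, half early, 1 SD) they give 23% and 34%. At the application's N = 200 the same scenario gives 39% and 61%.

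**Checks on the cause.** With no rise after onset (N = 200), the mean gives 4.6% and the peak 5.2%, so the inflation comes from post-onset samples. Across the second set, Day 1 alone gives 3.0-5.9%. A Day 3 landmark in patients still free of complications gives 3.0-7.3%.

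**Not computed.** The Poisson and length-of-stay models, and the effect of omitting arm, were not simulated.

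**Covariate list.** The same section defines injury outcomes as the incidence of pneumonia, ARDS, SIRS and MODS, then lists injury outcome as an adjustment variable. That puts what is being modelled on both sides of the equation.

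**The case against.** The strongest reply is that the text never says a mean, a peak or all five samples enter. It says only inflammatory markers, and a baseline predictor fits that wording. A reader might infer that post-onset samples are prescribed. They are not; they are merely not excluded. This stands and limits the point to what the plan permits.

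A reader might also infer that complications are counted only over the sampling days. Table 1 runs to 12 months, so some events may follow every sample. That lowers the bias, as the Days 1-14 rows show.

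The regression is also missing from SAP Section 7, and the application's Study Design text refers readers to the protocol for the full design. Aim 1 differs from the protocol on sample size (200 against 112) and on the cytokine method (t-tests against mixed models), so it may be out of date. This too stands, and it is why the first step is to ask whether the analysis survives. It does not dispose of the matter, because the text remains in the application.

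Early discharge could tie the number of samples to length of stay. That is minor, because eligibility requires an anticipated admission of at least 5 days.

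**Conclusion.** The point holds as a defect in a secondary analysis. Markers from Days 1-5 are named as predictors without limit, complications are recorded from the same Day 1, and arm is missing from the adjustment. Following that text permits reverse causation and drug-altered predictors.

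The size is uncertain. At N = 112 it runs from no visible inflation (about 5%) to false-positive rates of about 25-45% for a 5-day mean or peak, and beyond that if complications raise the markers more. It depends on the complication rate, the share of early onsets and the rise after onset, none of which the documents give.

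A reader might conclude that the trial's main result is compromised. The documents do not support that. The primary analysis compares log-transformed length of stay between randomised groups and uses no marker as a predictor, and the sample size rests on length of stay alone.

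**What to change.** State whether the marker regressions are still planned, and reconcile Aim 1 with Section 7, including the sample size. If they are withdrawn, say so.

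If they stand, put them in Section 7 with these rules:

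- The marker predictor is the pre-dose Day 1 sample defined in Section 10(e).
- Only complications with onset after that sample count. The Day 1 sample is free of inflation in the simulations because no onset precedes it there.
- Treatment arm is added to every model.
- Injury outcome is removed from the covariates.
- Day 2-5 markers are used only in a landmark analysis of patients still free of complications, or in a time-updated model, with samples drawn before onset.

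The change is to analysis wording; the pre-dose sample is already in the protocol, and the length-of-stay sample size does not move. The costs are that later samples leave the main predictive claim, patients with a complication before the first sample are excluded, and onset dates are needed. The documents do not say that onset dates are recorded, so this should be confirmed first.
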